The Impact of CBT-I on Cannabis Cessation Outcomes

[name], P.I.

NCT02102230

Study Protocol (last approved modifications)

06/29/2015

Title: The Impact of CBT-I on Cannabis Cessation Outcomes
Approval Period: 03/27/2015 - 03/11/2016

Modification

1. Summarize your proposed changes.
 
We would like to propose the following three changes to the current protocol.
 
 1. We would like to modify the study inclusion criteria to remove the requirement that individuals be motivated to quit cannabis at study baseline. This modification does not fundamentally alter the conceptual foundation of the study, the study design, hypothesis testing, or statistical power. We expect that individuals' motivation to use cannabis as a sleep aid will decrease following receipt of the interventions (relative to the control), leading to a reduction or cessation of cannabis use, consistent with existing hypotheses. We believe that this proposed modification will also increase ecological validity of the study, as a finding of a significant effect for CBT-I would allow for implementation of the intervention among all cannabis using individuals, regardless of initial desire to quit. 2. We would like to replace the overnight polysomnography-based sleep apnea assessment with a structured clinical interview for sleep apnea. Specifically, we propose to use the STOP-Bang (Chung et al., 2008) to screen for sleep apnea, within the context of the baseline assessment. Inclusion criteria will be modified from an AHI > 15 to a score on the STOP-Bang \geq 5. 3. Staff personnel have been updated. 
We request an expedited review of the proposed modifications as risk to participants is actually decreased (i.e., replacement of overnight sleep assessment with structured interview).

2. Indicate Level of Risk
 
Decrease

3. Update the Conflict of Interest (COI) section if any changes in COI have been made since the last protocol submission.
 
N Is there a change in the conflicting interest status for any existing personnel on this protocol?

Protocol Director				
Name [name]		Degree (program/year if student) Ph.D.		Title
Dept VAPAHCS, PTSD	Mail Code	[contact]	Fax [name]	E-mail [contact]
CITI Training current				Y

Admin Contact				
Name [name]		Degree (program/year if student) Ph.D.		Title
Dept VAPAHCS, PTSD	Mail Code	[contact]	Fax [name]	E-mail [contact]
CITI Training current				Y

Co-Protocol Director		

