The proposed study will employ a between subjects prospective design to follow 168 Veterans with CUD and co-occurring insomnia over the course of six months while individuals complete a treatment/placebo group within the context of outpatient addiction treatment at the Menlo Park division of the VA Palo Alto Health Care System. Overall, this design will involve assessments during the following times: baseline (prior to the intervention), over the course of the intervention, upon completion of the treatment/placebo group conducted during week 6 (completion of the sleep [or placebo] intervention), and three follow-up assessments conducted 2-weeks, 4-weeks, and 6-months post-treatment. Veterans will be recruited through the outpatient substance abuse treatment program within the Menlo Park Division of the VA Palo Alto Health Care System and through fliers placed throughout the community. Interested participants will complete a brief phone-based screening with a trained research assistant to assess for initial inclusionary/exclusionary criteria. Eligible individuals will then be scheduled for a baseline assessment once enough individuals have been recruited to comprise three groups for the treatment/placebo group portion. Baseline assessments will consist of structured clinical interviews, questionnaires, and a urine toxicology to assess for the presence/absence of marijuana. Eligible participants will then be randomly assigned to one of three conditions: (1) CBT-I with adjunctive sleep mobile app (CBT-I-MA); (2) CBT-I only (CBT-I); or (3) Placebo-control(PC). The treatment/placebo groups will occur weekly for six consecutive weeks. During this time, substance use (including

Title: The Impact of CBT-I on Cannabis Cessation Outcomes
Approval Period: 03/27/2015 - 03/11/2016

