(7) We will provide staff within veterans programs forms which they will distribute to individuals within their program. The forms will inquire if individuals are interested in hearing more about potential options for participating in research. They will be asked to check yes or no regarding their interest and provide their name and contact information. Study staff will collect the forms from the staff once/week and will contact those individuals indicating they were interested in research participation. This form can be found in section 16.

Patients interested in the study will contact the research laboratory to complete a brief phone screening for initial eligibility criteria and schedule a baseline appointment.

h) Inclusion and Exclusion Criteria.

Identify inclusion criteria.

To be included in the current study individuals must (1) be a Veteran 18 years or older; (2) meet DSM-5 diagnostic criteria for cannabis use disorder; and (3) meet DSM-5 diagnostic criteria for insomnia.

Identify exclusion criteria.

Individuals will be excluded based on evidence of the following: (1) inability to provide fully-informed written consent to participate; (2) history of, or current, psychotic symptoms or bipolar disorder; (3) current pregnancy; (4) sleep apnea as indicated by a score ≥ 5 on the STOP-Bang assessment; and (5) active suicidal/homicidal intent.

i) Describe your screening procedures, including how qualifying laboratory values will be obtained. If you are collecting personal health information prior to enrollment (e.g., telephone screening), please request a waiver of authorization for recruitment (in section 15).

Participants calling the laboratory with interest in the study will be briefly screened over the telephone to determine if they are likely to be study eligible. Likely eligible participants will be enrolled in the study and assessed for presence of cannabis use disorder, using the structured clinical interview for DSM-5, and insomnia (using the insomnia severity index). Participants who are positive for cannabis use disorder and insomnia, will be included in the study. Participants who are negative for cannabis use disorder or insomnia, will end study participation at this point.

j) Describe how you will be cognizant of other protocols in which participants might be enrolled. Please explain if participants will be enrolled in more than one study.

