Inclusion and exclusionary criteria was carefully considered in order to balance internal and external validity with minimal risk and greatest benefit to participants. To be included in the current study individuals must (1) be a Veteran 18 years or older scheduled to begin outpatient SUD treatment at VAPAHCS; (2) meet DSM-5 diagnostic criteria for cannabis use disorder; (3) meet DSM-5 diagnostic criteria for insomnia; (4) endorse a motivation to quit, evidenced by actively thinking about/or having a plan to quit in the next month; and (5) be willing to formalize and agree to a quit day which will occur after completion of the treatment/placebo group. Individuals will be excluded based on evidence of the following: (1) inability to provide fully-informed written consent to participate; (2) history of, or current, psychotic symptoms; (3) current pregnancy; (4) apnea hypopnea index (AHI) >15, indicative of moderate to severe sleep apnea; and (5) active suicidal/homicidal intent. Suicidal and homicidal intent will be assessed in the context of a structured clinical interview (see section 2a.3., “measures” subsection for details). In the case that respondents endorse active intent they will be referred immediately for treatment and will be excluded from the current study.

2a.3.f. Participant Retention.

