Hypothesis 1.1. Veterans who receive either *CBT-I-MA* or *CBT-I* prior to a cannabis cessation attempt will evidence a greater reduction in cannabis use frequency over the three post-quit attempt assessments (2-weeks, 4-weeks, and 6-months post-quit day) as compared to those who receive *PC*. In order to test this hypothesis a mixed-effects regression will be used to model changes in the dependent variable (frequency of cannabis use) across time as a function of group membership and baseline values (fixed effects) with a random effect for person to account for repeated measurements; frequency of cannabis use (obtained from TLFB; See 'measures' section for details).

As a secondary analysis, we will conduct an *analysis of covariance (ANCOVA; alpha set to .01)* to examine group differences in cannabis use frequency at each time point (2-weeks, 4-weeks, and 6-months post-cessation).

Hypothesis 1.2. Veterans receiving either *CBT-I-MA* or *CBT-I* will have greater point prevalence abstinence (PPA) over the three post-quit attempt assessments (2-weeks, 4-weeks, and 6-months post-quit day) compared to those receiving *PC*. In order to test this aim we will evaluate the differences in PPA between *CBT-I-MA* and both *CBT-I* and *PC* groups, and *CBT-I* and *PC* groups across the three follow-up assessments (2-weeks, 4-weeks, and 6-months post-cessation). This will be conducted through the use of a mixed-effects logistic regression.

As a secondary analysis, we will conduct three chi-square analyses to examine group differences in rates of PPA at each of the three time points (2-weeks, 4-weeks, 6-months post-cessation).

Exploratory Hypothesis. *In terms of the above cannabis outcomes, those who receive CBT-I-MA will evidence better outcomes (reduced frequency and greater PPA) as compared to those who receive CBT-I. Results related to this hypothesis will be determined through analyses conducted for the primary hypotheses (Hypothesis 1.1 and 1.2).*

Secondarily, we will conduct exploratory analyses to examine factors (e.g., adherence, dose) that account for differences observed between the *CBT-I-MA* and *CBT-I* groups in relation to cannabis outcomes through the use of mediation models. Mediators of interest will include adherence (measured by session attendance), and dose.

Aim 2:

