In terms of the primary hypothesis of Aim 1 (Hypothesis 1.1), *the impact of CBT-I-MA and CBT-I on frequency of cannabis use post-cessation, we based our power calculations on an ANCOVA with the inclusion of 3 covariates as this would provide an overestimation of the sample size required for the GLMM analysis. A sample of 168 individuals would allow for a detection of a significantly smaller effect in terms of the primary aim ($d = .42$), providing confidence in our ability to detect the hypothesized effect of $d = 1.4$. This sample size will also allow for adequate power to detect group differences between CBT-I-MA and CBT-I ($d = .42$; Aim 1 Exploratory Hypothesis)*.

In terms of the secondary hypothesis of Aim 1 (Hypothesis 1.2), *the impact of CBT-I-MA and CBT-I on PPA, we used power calculation software to calculate the effect size based on a test of independent proportions. With an estimated abstinence rate of 20% within the placebo condition (PC; based on previous research; Marijuana treatment project research group, 2004), and alpha of .05, 168 Veterans (56 per group) will allow for power of .80 to detect a 30% difference in the prevalence of abstinence in the CBT-I group. As we conservatively estimate a 50% abstinence rate in the CBT-I condition, we will have enough power to detect the expected effect*.

In terms of Aim 2, investigating the role of CBT-I-MA and CBT-I on subjective and objective sleep quality, *we based our power analysis on an ANCOVA with the inclusion of 3 covariates and 3 groups as this would overestimate the required sample size needed within GLMM models. A sample of 168 individuals would allow for a detection of a smaller effect in terms of the primary aim ($d = .42$), providing confidence in our ability to detect the hypothesized conservative effect of $d = .56$. This will also allow for adequate power to detect group differences between CBT-I-MA and CBT-I ($d = .42$; Aim 2 Exploratory Hypothesis)*.

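### The motivation requirement was dropped and the current protocol has no quit day, but the SAP still tests post-quit hypotheses and the power claim has no calculation behind it

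*Protocol*

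**What the plan says.** **Protocol.** Item 1 of the Modification section proposes to "remove the requirement that individuals be motivated to quit cannabis at study baseline". It then asserts: "This modification does not fundamentally alter the conceptual foundation of the study, the study design, hypothesis testing, or statistical power". Its reasons are that the interventions should lower the motivation to use cannabis as a sleep aid, and that ecological validity should improve. Items 2 and 3 concern apnea screening and staff.

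Section 8h now has three inclusion criteria: being an adult Veteran, and to "meet DSM-5 diagnostic criteria for cannabis use disorder; and (3) meet DSM-5 diagnostic criteria for insomnia". Motivation and a quit day are not among them. Section 2a describes "three follow-up assessments conducted 2-weeks, 4-weeks, and 6-months post-treatment" and contains no quit attempt.

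**SAP.** The only statistical plan is abstracted from a grant application whose funding notice is dated February 2014, before the modification. Section 2a.3.e requires participants to "endorse a motivation to quit, evidenced by actively thinking about/or having a plan to quit in the next month" and to agree a quit day after the group programme. Section 2a.3.g tells them to attempt to quit on the day after the post-group assessment. Section 2a.3.j words H1.1 as "a greater reduction in cannabis use frequency over the three post-quit attempt assessments (2-weeks, 4-weeks, and 6-months post-quit day"). H1.2, H2.1 and H2.2 use the same post-quit assessments.

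For H1.2 the Power Analysis starts: "With an estimated abstinence rate of 20% within the placebo condition". It sets this against 50% under CBT-I, with 56 per group and alpha .05, and states power of .80.

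**The concern.** Three things do not fit together.

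- **Time origin and population.** The hypotheses are counted from a quit day that the current protocol does not contain, in participants selected by a criterion that no longer applies. An analyst would have to decide, possibly with data in hand, whether to count from the end of treatment or from a quit attempt, and whether to include people who never tried to stop.
- **Rationale.** SAP section 2a.3.a places CBT-I before the quit attempt because insomnia affects lapse most in the first 48 hours of an attempt. The modification relies on another route, a weaker wish to use cannabis for sleep. That route may be sound, but the treatment effect it implies is on cannabis use whether or not anyone sets out to quit.
- **Power and precision.** The H1.2 rates were set for a population that the SAP describes as self-motivated to quit. If some participants now have no intention to stop, abstinence may be lower in both arms and the difference smaller. Baseline motivation, once restricted by eligibility, is now free to vary. It is in neither cannabis model and not among the potential confounders in SAP Table 1, so the planned check for imbalance would not cover it.

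**Working it through.** **1. The two documents side by side**

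| Item | SAP | Current protocol |
|---|---|---|
| Entering SUD treatment | Required (2a.3.e) | Not a criterion (8h); setting still outpatient addiction treatment, plus community fliers (2a) |
| Motivation to quit | Required (2a.3.e); ladder screens out low motivation (2a.3.i) | Not a criterion (8h) |
| Quit day | Required (2a.3.e), with an instructed attempt (2a.3.g) | Absent (2a, 8h) |
| Follow-up counted from | Quit attempt | End of treatment (2a) |
| Hypotheses and power | Post-quit; 20% v 50% for H1.2 | Not restated or recalculated |

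The Funding section of the protocol nevertheless answers yes when asked whether its contents match the federal proposal.

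**2. The SAP's H1.2 figure**

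Inputs (SAP, Power Analysis): p1 = .20, p2 = .50, n = 56 per arm, alpha .05. Two-sided testing is assumed, since the SAP does not say. For the pooled-variance two-proportion test:

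power = Φ{ [|p2 − p1|√n − 1.96√(2p̄(1 − p̄))] / √(p1(1 − p1) + p2(1 − p2)) }

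With p̄ = .35: [.30 × 7.483 − 1.96 × .6745] / .6403 = (2.245 − 1.322) / .6403 = 1.44, so power = .925. Power of .80 needs 39 per arm.

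The stated .80 is therefore not reproduced, and it errs on the cautious side. Alpha .01 would give .786, but the text says .05.

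**3. The margin**

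With 56 per arm, the smallest difference detectable with power .80 is 24.5 points from a 20% control rate, 21.2 points from 10% and 18.2 points from 5%.

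**4. Dilution scenarios**

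The documents give no abstinence rates for unmotivated users, so each row is an assumption. The 45-per-arm column uses the 80% follow-up in SAP 2a.3.f: 168 × .80 / 3 = 44.8.

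| Assumption | Control v CBT-I | Power, 56 per arm | Power, 45 per arm |
|---|---|---|---|
| SAP rates | 20% v 50% | .93 | .86 |
| 75% motivated, the rest abstain in neither arm | 15% v 37.5% | .78 | .69 |
| 50% motivated, the rest abstain in neither arm | 10% v 25% | .55 | .46 |
| Odds ratio 4, control 10% | 10% v 30.8% | .79 | .69 |
| Odds ratio 4, control 5% | 5% v 17.4% | .55 | .46 |
| 30-point gap kept | 10% v 40% | .97 | .92 |

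Rows 2 and 3 multiply both planned rates by the motivated share, for example .75 × 20% = 15% and .75 × 50% = 37.5%. The odds ratio of 4 is the planned one: (.50/.50) / (.20/.80) = 4. At a control rate of 10%, the odds are .111 × 4 = .444, and .444/1.444 = 30.8%.

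Worked example, row 2: p̄ = .2625, and [.225 × 7.483 − 1.96 × .6222] / .6016 = .77, so power = .78.

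**The case against.** Much of the case on the other side stands, and it rules out several stronger readings.

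- **A reader might infer that the modification removed motivated quitters and the quit day.** It removed a requirement, so motivated Veterans remain eligible. The quit day is not in the list of changes, and the documents do not show when or why it left the protocol. The wider recruitment routes came through separate changes at the March 2015 renewal.
- **A reader might infer that the trial now takes all comers.** Protocol section 2a still places it within outpatient addiction treatment, and section 8c still speaks of people seeking such treatment. That is a tension within the protocol, not a clean switch.
- **A reader might infer that the whole trial was powered on quitters.** N = 168 comes from a mediation calculation. The effect of d = .56 concerns sleep in psychiatric comorbidity, and d = 1.4 concerns withdrawal-related sleep. The 50% rate has no cited source. The 20% rate cites a marijuana treatment project whose participants the documents do not describe. The calculation above therefore concerns H1.2 only, which the SAP calls the secondary hypothesis of Aim 1.
- **Relapse has no meaning for someone who never quit.** That is true, but no hypothesis is worded on relapse. Use frequency and point prevalence abstinence can be measured without a quit attempt.
- **The shift in days is small.** Under the SAP the attempt falls one day after the post-group assessment. The anchor therefore matters for what is estimated and in whom, more than for visit timing.
- **The figures are for a single time point.** The planned H1.2 model uses three assessments and all available data, so the 45-per-arm column is pessimistic about missing data.

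The sponsor also wrote that power is not fundamentally altered, which is weaker than saying it is unchanged. What remains is that no calculation supports even that, and that the SAP's eligibility and hypotheses do not match the protocol in force.

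**Conclusion.** The mismatch is documented and needs correcting: all four Aim 1 and Aim 2 hypotheses are counted from an event that the current protocol does not contain.

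On power, the supportable conclusion is narrower. It would be tempting to say that the modification left H1.2 underpowered, but the documents do not show that. At the SAP's own rates there is spare power (.93 against a stated .80). A control rate of 10% with the planned odds ratio still gives .79, and a preserved 30-point gap gives .97. The margin is used up when about a quarter of the sample is unmotivated and abstains in neither arm (.78), and it fails clearly at one half (.55) or at a 5% control rate with odds ratio 4 (.55). The statement on power is thus unsupported rather than shown to be false.

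These results assume a two-sided .05 pairwise comparison at one time point, 56 per arm, and abstinence rates that are ours. The value of adjusting for motivation rests on its predicting abstinence, which is plausible but not evidenced in the documents. Randomisation protects the comparison in either case.

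**What to change.** Issue an SAP addendum; the submitted modification form need not be edited.

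1. Reconcile the SAP's eligibility criteria and time anchor with the current protocol, and explain the unlisted loss of the quit day. Restate H1.1, H1.2, H2.1 and H2.2 at 2 weeks, 4 weeks and 6 months post-treatment in all randomised participants, whether or not a quit attempt was made.
2. Add the baseline motivation ladder score as a fixed covariate in the H1.1 and H1.2 models. SAP Table 1 schedules a ladder at baseline, and protocol section 16 lists a Marijuana Ladder attached in December 2014. Confirm first that it is still administered at baseline and that earlier participants, if any, have a score. Add a before/after-modification indicator only if participants were enrolled before the change.
3. Replace the statement on power with a sensitivity table for H1.2 over control abstinence rates of 5% to 20%, with the rates labelled as assumptions.

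The cost is SAP wording, one or two covariates and a short table. No new instrument is needed if the ladder is still in use. The stated power may look less favourable, and there is a little more analysis work.

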d) Please describe an adequate plan to destroy the identifiers at the earliest opportunity consistent with conduct of the research, unless there is a health or research justification for retaining the identifiers or such retention is otherwise required by law.

Research records will be maintained and then disposed of consistent with VA record retention policies.

16. Attachments

Attachment Name	Attached Date	Attached By	Submitted Date
Funded Grant Proposal	02/04/2014	[name]	
VA required questions	02/04/2014	[name]	
Appointment Reminder	02/04/2014	[name]	
Demographics	02/11/2014	[name]	
SCID	02/11/2014	[name]	
Fear of Sleep	02/11/2014	[name]	
Epworth Sleepiness Scale	02/11/2014	[name]	
PSQI	02/11/2014	[name]	
PSQI addendum	02/11/2014	[name]	
DBAS	02/11/2014	[name]	
ISI	02/11/2014	[name]	
sleep diary	02/11/2014	[name]	
Berlin	02/11/2014	[name]	
Fagerstrom	02/11/2014	[name]	
MEQ	02/11/2014	[name]	
MCQ	02/11/2014	[name]	
MSE	02/11/2014	[name]	

Title: The Impact of CBT-I on Cannabis Cessation Outcomes

Approval Period: 03/27/2015 - 03/11/2016

CUDIT	02/11/2014	[name]	
AUDIT	02/11/2014	[name]	
CMMQ	02/11/2014	[name]	
MSHQ	02/11/2014	[name]	
TLFB alc	02/11/2014	[name]	
TLFB mj	02/11/2014	[name]	
TLFB cigs	02/11/2014	[name]	
PMI	02/11/2014	[name]	
MWC	02/11/2014	[name]	
UPPS	02/11/2014	[name]	
EMQ	02/11/2014	[name]	
DQ	02/11/2014	[name]	
EA	02/11/2014	[name]	
DERS	02/11/2014	[name]	
PCL/LES	02/11/2014	[name]	
DT	02/11/2014	[name]	
ASI	02/11/2014	[name]	
IDAS	02/11/2014	[name]	
PANAS	02/11/2014	[name]	
IPF	02/11/2014	[name]	
TEF	02/11/2014	[name]	
BABAS	02/11/2014	[name]	
IPAQ	02/11/2014	[name]	
KIMS	02/11/2014	[name]	
SDS	02/11/2014	[name]	
DPSS-R	02/11/2014	[name]	
CEQ	02/11/2014	[name]	
TEQ	06/17/2014	[name]	
MAUM	08/14/2014	[name]	

Title: The Impact of CBT-I on Cannabis Cessation Outcomes
Approval Period: 03/27/2015 - 03/11/2016

PBN DMC [name] acceptance memo 6-19-14	08/14/2014	[name]	
CoC_Final	08/14/2014	[name]	
Marijuana Ladder	12/19/2014	[name]	
recruitment sheet	03/05/2015	[name]	
social media script	03/24/2015	[name]	
Flyers	03/24/2015	[name]	
Apnea Assessment	03/24/2015	[name]	

Obligations

The Protocol Director agrees to:

- Adhere to principles of http://humansubjects.stanford.edu/research/documents/eval_study_designGUI03017.pdf sound scientific research designed to yield valid results
- Conduct the study according to the protocol approved by the IRB

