The Impact of CBT-I on Cannabis Cessation Outcomes

[name], P.I.

NCT02102230

**Research Design and Statistical Plan sections
abstracted from CDA application**

Notice of Intention to Fund: 02/24/2014

2a.3. Research Design and Methods

Design Framework.

The proposed study will employ a between subjects prospective design to follow 168 Veterans with CUD and co-occurring insomnia over the course of six months while individuals complete a treatment/placebo group followed by a cannabis cessation attempt within the context of outpatient addiction treatment at the Menlo Park division of the VA Palo Alto Health Care System. Overall, this design will involve assessments during the following times: baseline (prior to the intervention and quit attempt), *over the course of the intervention*, upon completion of the treatment/placebo group conducted during week 6 (completion of the sleep [or placebo] intervention), and three follow-up assessments conducted 2-weeks, 4-weeks, and 6-months post-cessation. Veterans will be recruited through the outpatient substance abuse treatment program within the Menlo Park Division of the VA Palo Alto Health Care System. Interested participants will complete a brief phone-based screening with a trained research assistant to assess for initial inclusionary/exclusionary criteria. Eligible individuals will then be scheduled for a baseline assessment once enough individuals have been recruited to comprise three groups for the treatment/placebo group portion. Baseline assessments will consist of structured clinical interviews, questionnaires, and a lab-based physiological sleep assessment. Eligible participants will then be randomly assigned to one of three conditions: (1) *CBT-I with adjunctive sleep mobile app (CBT-I-MA)*; (2) *CBT-I only (CBT-I)*; or (3) *Placebo-control (PC)*. The treatment/placebo groups will occur weekly for six consecutive weeks. *During this time, substance use (including cannabis) and sleep will be monitored*. Upon completion of the treatment/placebo group (week 6), individuals will complete self-report questionnaires and a sleep assessment. Individuals will then schedule their cessation attempt for the following day. Two-weeks, 4-weeks, and 6-months post-cessation (follow-up assessments) participants will complete home-based sleep assessments (actigraphy) and the same self-report and interview-based questionnaires that were administered during baseline. Assessments will be completed in person. Baseline and 6-month follow-up interviews and questionnaires will take 3 hours to complete, while 2-week and 4-week post-cessation follow-up appointments will take 1 hour. Home-based sleep assessments will occur overnight for the length of each individual's typical sleep cycle (approximately 8 hours).

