Motivation to Quit: Motivation to quit cannabis will be assessed using an adapted version of the Contemplation Ladder (CL) developed for tobacco cessation (Prochaska & DiClemente,

1983). The CL is a visual analogue scale comprised of 10 steps, each with a corresponding statement assessing motivation to quit cannabis. *The CL will be used to assess both inclusionary (those planning to quit within the next 30 days), and exclusionary (those with little to no motivation to quit) criteria.*

Obstructive Sleep Apnea: Initial screening for obstructive sleep apnea (OSA) will be conducted using the Berlin Questionnaire (Netzer et al., 1999). This measure assesses known risk factors for OSA, and consists of self-report questions indexing snoring (5 questions), daytime sleepiness (3 questions), history of high blood pressure (1 question), and information on age, sex, body mass, neck circumference, and ethnicity. Based on responses to these symptom categories, level of risk for OSA is determined based on the following criteria: Category 1: "high risk" includes persistent symptoms (>3 to 4 times/week) in 2 or more questions about snoring. Category 2: "high risk" includes persistent symptoms (>3 to 4 times/week) of sleepiness, drowsy driving, or both. Category 3: "high risk" includes history of high blood pressure or a BMI of more than 30 kg/m². In order to meet criteria for "high risk," individuals must qualify for at least 2 of the above high risk categories. Those not meeting these criteria are deemed "low risk." Objective confirmation of OSA will be conducted during the intake polysomnography assessment (see below for details). Consistent with methods of scoring set forth by the American Academy of Sleep Medicine, apneas will be defined as complete absence of airflow, while hypopneas are defined as a greater than 50% reduction in chest excursion and a 3% oxygen desaturation, or greater than 50% decrease in chest excursion and arousal. AHI will be calculated. Consistent with published guidelines, the following scoring scheme will be employed: mild OSA (AHI: 5-14.9), moderate OSA (AHI:15-29.9), and severe (AHI >/= 30). *Individuals with an AHI of 15 or greater will be excluded.*

Measures: Cannabis Use.

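### After the 2015 entry change no planned analysis looks at baseline motivation to quit, so a significant average effect would not show benefit regardless of desire to quit

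*Protocol*

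**What the plan says.** **The change.** The Protocol's Modification section, item 1, proposes to "remove the requirement that individuals be motivated to quit cannabis at study baseline". It states that "This modification does not fundamentally alter the conceptual foundation of the study, the study design, hypothesis testing, or statistical power", and that a significant finding "would allow for implementation of the intervention among all cannabis using individuals, regardless of initial desire to quit". The current inclusion criteria (Protocol 8h) accordingly contain no motivation item.

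**The analysis plan.** The SAP is abstracted from the funding application and dated "Notice of Intention to Fund: 02/24/2014", so it predates the change. Its entry criteria (2a.3.e) still require participants to "endorse a motivation to quit, evidenced by actively thinking about/or having a plan to quit in the next month".

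**The measure.** SAP 2a.3.i says: "Motivation to quit cannabis will be assessed using an adapted version of the Contemplation Ladder (CL) developed for tobacco cessation". The only use described is deciding who enters. Table 1 schedules the ladder at baseline only, under inclusion and exclusion criteria, and does not list it among the potential confounding factors. The current Protocol lists a form called "Marijuana Ladder" in section 16, attached 12/19/2014. Its body text does not say whether or when the form is given.

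**The models.** H1.1 (SAP 2a.3.j) has group, baseline values and a random person effect. H1.2 is a mixed-effects logistic regression with no covariates named.

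**The nearest provisions.** SAP 2a.3.a, 2a.3.i and 2a.3.j each provide for exploring baseline factors as moderators, but only where the groups differ on them. The power section assumes three covariates and does not name them.

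**The concern.** While motivation was an entry criterion, its range was narrow and it made sense to use the ladder only as a gate. With the criterion removed, motivation can run from none to ready to quit, and the ladder has lost its only stated purpose.

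The Modification's reason for the change is that a positive result could be applied whatever a person's wish to quit. The planned tests estimate one average effect per comparison. An average can be clearly positive while the effect is absent among those with little wish to quit, who are the group the change newly admits. As planned, the report would carry no estimate that bears on that group. A smaller cost is some lost precision if motivation predicts cannabis use beyond baseline use.

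**Working it through.** **Inputs from the SAP:** 168 randomised, 56 per arm; alpha .05 (two-sided assumed, since sidedness is not stated); abstinence 20% v 50%; hypothesised d = 1.4 and stated detectable d = .42 for cannabis use frequency; 80% completing all follow-ups. **Assumed, because the documents give no figure:** the share of participants with low motivation (20–50%), and the outcome variance explained by the ladder beyond baseline use (R² = .05–.20).

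**1. The plan's own figure.** For 20% v 50% at 56 per arm, the two-proportion normal formula gives power .925 (.891 with continuity correction), against a stated .80. With continuity correction and 20% loss (45 per arm) it gives .801, so the stated .80 can be reproduced on that basis. For d = .42 at 56 v 56 with no covariates, noncentral-t power is .596.

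**2. Can the average be significant with no benefit at low motivation?** Let the effect be 1.4 SD in motivated participants and zero in a share q. The average effect is 1.4(1 − q).

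| q | average d | power, 56 v 56 |
|---|---|---|
| 20% | 1.12 | 1.00 |
| 30% | 0.98 | .999 |
| 50% | 0.70 | .96 |

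A mixed effect also widens the treated arm's variance to 1 + 1.4²q(1 − q). At q = 50% that is 1.49, so SE = √((1.49 + 1)/56) = 0.211, 0.70/0.211 = 3.32, and power = Φ(3.32 − 1.96) = .91. A significant result is therefore fully compatible with no benefit in half the sample.

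**3. The same dilution applied to abstinence.** The CBT-I rate becomes 20% + 30%(1 − q), that is 44%, 41% and 35%. Power falls from .925 to .785, .679 and .427. The statement that power is not fundamentally altered thus relies on the effect not depending on motivation.

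**4. Would the existing clauses catch it?** They act only when arms differ at baseline. Imbalance between arms and variation of the effect with motivation are unrelated: perfectly balanced arms can hide a strong interaction. For scale, the chance that two arms of 56 differ by 0.25 SD or more on the ladder is 2[1 − Φ(0.25/√(2/56))] = .19.

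**5. Gain from adjusting (continuous outcome, d = .42, 56 v 56).** Residual SD is √(1 − R²), and the equivalent gain in sample size is 1/(1 − R²).

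| R² | power | equivalent gain in N |
|---|---|---|
| 0 | .596 | – |
| .05 | .618 | 5% |
| .10 | .641 | 11% |
| .15 | .666 | 18% |
| .20 | .693 | 25% |

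**6. Precision of one interaction, pooled CBT-I arms v PC.** With ladder and residual SD both set to 1, the SE of the slope difference is √(1/112 + 1/56) = 0.164, so the 95% half-width is 1.96 × 0.164 = 0.32 SD of outcome per SD of ladder. At 80% retention it is 0.32/√0.8 = 0.36.

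**The case against.** **The sentence is a rationale to the ethics board, not an analysis claim.** If no motivation screen is applied at entry, the average effect in the enrolled sample is the relevant evidence for offering CBT-I without such a screen. This stands. A reader might infer that the generalisation has no support at all, and the documents do not bear that out. Only the reading that benefit holds at each level of motivation outruns the plan.

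**The SAP is not silent on baseline factors.** The general clause in 2a.3.a is broad enough to reach motivation, and the three unnamed covariates could include it. True, but the clause depends on imbalance, and the covariates belong to a power calculation that commits the analyst to nothing.

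**Motivation may matter little.** A reader might infer that a strong predictor has been left in the error term. The documents give no correlation between motivation and outcome, H1.1 already adjusts for baseline values, and at R² of .10 or less the gain is under 5 points of power. At the hypothesised d = 1.4, power at 56 v 56 is essentially 1 with or without the ladder. Nor does the omission bias a randomised comparison.

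**The ladder may no longer be given.** Fair. Continued use is inferred from the 2014 Table 1 and from an attachment. Section 16 also still lists the Berlin form, although the current text screens apnea with the STOP-Bang, so an attachment does not prove current use. Most other measures were attached on 02/11/2014, so ladder data on the earliest participants are unconfirmed too.

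**The interaction will be imprecise.** Also fair. With 56 v 56 and the ladder split into low and high, power for an interaction of .42 SD is only .14 to .20.

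**Conclusion.** The point holds in a limited form. No planned analysis names baseline motivation, and the conditional moderator clauses respond to the wrong trigger. A significant average effect would support benefit in the enrolled mix, and the phrase about desire to quit goes further than that. The illustration (power of at least .91 with no benefit in half the sample) rests on the plan's d = 1.4 and an assumed low-motivation share. It shows what the test cannot rule out and does not predict that the effect varies.

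The precision argument is secondary: 2 to 10 points of power at d = .42 for an assumed R² of .05–.20, worked for the continuous outcome only. The primary comparison remains valid without the change. The case for acting is that the improvement is specific and close to free, provided that the ladder is being collected.

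**What to change.** 1. Confirm that the ladder is given to every participant before randomisation, and state this in the Protocol. Establish whether those enrolled before the form was attached have a score.
2. Pre-specify the baseline ladder score as a covariate in H1.1 and H1.2. In H1.2 report the adjusted effect as a marginal risk difference, or state that the odds ratio is conditional on the ladder, because adding a covariate to a logistic model changes the odds ratio being estimated.
3. Pre-specify one exploratory interaction, pooled CBT-I arms v PC by ladder score. Report it with its confidence interval whether or not the arms differ at baseline.
4. Word the conclusion as the average effect in the enrolled mix, with no claim of benefit at each level of motivation.

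**Cost.** SAP wording, and one Protocol sentence, if the ladder is already collected; otherwise one brief form at the baseline visit. The interaction will be imprecise (half-width about 0.32 SD per SD, 0.36 at 80% retention). It should be labelled as estimation and not used for confirmatory claims in either direction.
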